4.1.10. Double-Blind (DB) Baseline Value

DB baseline values will be defined as the baseline values from SZ-001 double-blind study.

4.1.11. Extension Baseline Value

For purposes of analysis, the baseline value is defined as the last value obtained prior to initiation of IMP in CVL-865-SZ-002 (e.g. the Study Day 1 value). Should the Day 1 visit value be obtained after the first dose of IMP or if this value is not available at Day 1, then the most recent value obtained prior to earliest initiation of IMP will be used for the baseline value.

4.1.12. Last Dose of IMP

Last Dose of IMP is defined as the last date that the subject received IMP.

4.1.13. Overdose

Overdose is any dose of CVL-865 greater than 80 mg within a 24-hour time period (+2 hours).

4.1.14. Change from Baseline (Extension)

Change from baseline for a given endpoint is defined as the value on a given Study Day (time point) minus the Baseline Value.

4.1.15. Change from Double-Blind Baseline

Change from double-blind baseline for a given endpoint is defined as the value on a given Study Day (time point) minus the double-blind Baseline Value.

4.1.16. Cumulative Dose of IMP (Extension)

The cumulative dose of IMP is calculated in milligrams and is based on the daily dose of IMP as recorded in the EXPOSURE CRF.

4.1.17. Cumulative Dose of IMP (Double-Blind + Extension)

The cumulative dose of IMP is calculated in milligrams and is based on the daily dose of IMP as recorded in the EXPOSURE CRF.

4.1.18. Compliance with Study Drug (Extension)

Dosing compliance based on daily dose of IMP as recorded in the EXPOSURE CRF will be defined by the dosing compliance ratio: the number of doses actually taken by the subject divided by the number of doses that were expected to be taken during the same period multiplied by 100. If poor compliance is encountered (e.g., multiple missed doses resulting in less than 80% overall compliance at any point in the trial), discontinuation of the subject from the trial should be considered. Subjects who habitually miss visits or habitually attend visits outside of the protocol-defined visit window are also defined as noncompliant and should be considered for discontinuation.

4.1.19. Diary Days

Diary days are defined as days with completed ediary assessments.

4.1.20. Diary Compliance

Diary compliance will be calculated as 100 times the number of diary days (i.e., days with completed diary assessments) during the period and dividing this quantity by the expected number of diary days that should have been completed during this period.

4.1.21. Handling of Missing Severity or Relationship for Adverse Events

Adverse events with missing severity will have the severity imputed as 'Severe'. Adverse events with missing relationship to CVL-865 will have the relationship imputed as 'Related' if the AE started after the first CVL-865 dose in CVL-865-SZ-002.

Actual values will be presented in the data listings.

4.1.22. Handling of Incomplete or Missing Dates

An incomplete date occurs when the exact date an event occurred or ended cannot be obtained from a subject. The database contains data fields for month, day, and year. A date is incomplete if at least one of these three fields is not known.

For many of the planned analyses, a complete date is necessary to determine if the event should be included in the analysis (e.g. if the event is treatment-emergent) or to establish the duration of an event. In such cases, incomplete dates will be imputed.

For the purposes of handling partially reported start and stop dates for an event the following algorithm will be applied:

- Missing start day, but month and year present:
If the event occurs same month and year as the occurrence of IMP, then the start day of the event will be assigned to the day of first dose of IMP (i.e., Day 1).
Otherwise, the start day will be set to the first day of the month.
- Missing start day and month, but year present:
If event occurs in the same year as IMP, then the start date of the event will be assigned to Day 1.
Otherwise, the start day and month will be set to 01 January.
- In the unlikely event of a completely missing start date (year not present), the start date will be imputed as Day 1.
- Missing end day, but month and year present:
The day will be set to the last day of the month.
- Missing end day and month, but year present:
The end day and month will be set to the date of study completion.
However, if study completion year is greater than the year of the event, then the day and month will be set to 31 December.
- Missing all components of an end date and the event is not marked as ongoing:
The event will be considered as 'ongoing' and will be considered treatment-emergent if the start date is on or after Day 1.

If any imputed date causes the end date to occur prior to the start date of the event, the start date of the event will be used for the imputation of the end date. If the imputed date is later than the date of study withdrawal, then the date of study withdrawal will be imputed for the date. In subject data listings, start and stop date of events will be displayed as reported on the eCRF (i.e., imputed values will not be listed).

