3.2.7.3. Prior Medications

Prior medications are those medications taken prior and ended prior to the initiation of IMP. These medications will be recorded in the CONCOMITANT MEDICATION eCRF.

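### SAP 4.1.22 can turn an event that ended before Day 1 into a treatment-emergent one, and its Day 1 trigger does not say first dose

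*SAP*

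**What the plan says.** SAP 4.1.22 has three rules that can place an onset on Day 1.

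- **Day missing.** The trigger is "If the event occurs same month and year as the occurrence of IMP". The value assigned is the day of first dose. If the trigger is not met, the first of the reported month is used.
- **Day and month missing.** "If event occurs in the same year as IMP, then the start date of the event will be assigned to Day 1". If not, "Otherwise, the start day and month will be set to 01 January".
- **Everything missing.** "In the unlikely event of a completely missing start date (year not present), the start date will be imputed as Day 1".

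None of the three refers to the reported end date. A closing clause covers conflicts: when any imputed date leaves the end earlier than the start, "the start date of the event will be used for the imputation of the end date". The start is not reconsidered. Listings keep the dates as reported, so the imputed values appear only through the tables.

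SAP 3.2.1.3 makes an event treatment-emergent if its onset is on or after first IMP. SAP 5.12.1 uses the imputed onset for that decision and also plans a table of adverse events by dose at onset. SAP 3.2.7.3 says "Prior medications are those medications taken prior and ended prior to the initiation of IMP".

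**The concern.** There are two separate faults.

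**End date ignored.** A reported end before Day 1 is firm evidence that the event was over before extension treatment began. The rules overwrite that evidence. An onset assumed to be Day 1 takes precedence over an end date that was actually recorded, and the event enters the TEAE tables. That defeats the SAP's own pre-treatment category (SAP 3.2.1.2).

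**Trigger undefined.** The year rule and the month rule test against IMP, or its occurrence, without saying first dose or naming the trial. Elsewhere the SAP is specific: 4.1.3 and 4.1.21 both refer to first dosing in CVL-865-SZ-002. IMP is taken for up to 57 weeks, so the year of IMP is not a single year.

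Temporality of TEAEs is part of the primary endpoint (Protocol Section 3). An onset moved to Day 1 looks like an early event. In the dose-at-onset table it is charged to the first titration dose: 5 mg BID for former placebo subjects and 12.5 mg BID for former 7.5 mg BID subjects, rather than the 25 mg BID maintenance dose (SAP Table 1).

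**Working it through.** The plan gives no figure to reproduce here, so the check applies the rules as written.

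**1. End-date rule.** Take Day 1 = 15 Sep 2021 (an illustrative date).

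| Reported start | Reported end | Start after rule | End after conflict clause | TEAE? |
|---|---|---|---|---|
| Sep 2021, day missing | 13 Sep 2021 | 15 Sep 2021 | 15 Sep 2021 | Yes |
| 2021 only | 20 Aug 2021 | 15 Sep 2021 | 15 Sep 2021 | Yes |
| Completely missing | 13 Sep 2021 | 15 Sep 2021 | 15 Sep 2021 | Yes |

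All three events ended before Day 1. The results are the same whether the trigger means first dose or any dosing, because September 2021 and 2021 contain the first dose. Partial end dates are imputed late (last day of the month, 31 December or study completion), so the conflict clause bites mainly when the start has been pushed forward to Day 1.

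**2. Does treatment always span two calendar years?** 57 weeks × 7 = 399 days, and the end-of-taper visit is nominally Day 400. Since 400 > 366, a full course always crosses a year-end. For the 365 possible Day 1 dates in 2021, 331 give two calendar years of dosing and 34 (28 November onward) give three.

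**3. Year-only onsets under the two readings.** Every Day 1 date was paired with every study day to Day 428: 365 × 428 = 156,220 onsets, equally weighted, each reported by year only, with dosing on Days 1 to 400.

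| | First-dose year | Any year with dosing |
|---|---|---|
| Moved to an earlier calendar year | 0 | 89,019 (89,019/156,220 = 57%) |
| Mean shift from true onset | 130 days | 212 days |
| Largest shift | 364 days | 427 days |
| TEAE status changed | 0 | 0 |

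TEAE status never changes because both the true and the imputed onset are on or after Day 1.

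**4. One case.** Day 1 = 15 Sep 2021; true onset 10 Mar 2022 (Day 177), reported as 2022. The first-dose reading gives 1 Jan 2022 (Day 109). The any-dosing reading gives 15 Sep 2021 (Day 1), which contradicts the reported year. If the onset is reported as March 2022, the first-dose reading gives 1 Mar 2022 and the any-dosing reading again gives 15 Sep 2021.

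**The case against.** **The first-dose reading is the natural one.** The month rule assigns the day of first dose. If its trigger covered any month of dosing, every on-treatment event lacking only its day would go to Day 1, which is hardly intended. This stands. A reader might infer that the SAP does send later-year events back to Day 1. The text permits that but does not establish it, so this part is an ambiguity to close, not a demonstrated error. Yet two programmers following SAP 9.3 could code it differently.

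**Imputation applies only where needed.** SAP 4.1.22 imputes when a complete date is required to decide inclusion or duration, and a reported end before Day 1 already decides that an event is not treatment-emergent. This is sensible, but the algorithm does not say it, and the conflict clause applies to any imputed date. If that clause were confined to imputed end dates, the onset would still be Day 1 and the record would end before it began.

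**Few adverse events qualify.** Collection starts at consent, scheduled at Visit 1 on Day 1, so almost no scheduled time exists for an event to end before first dose. This stands and limits the scope.

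**Medications are not named.** The algorithm speaks of events, and SAP 3.2.7.3 would keep a medication with a reported pre-Day 1 end as prior. The error reaches medications only if the programmers apply the event algorithm to them.

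**Day 1 is conservative, and the trial is descriptive.** Leaning toward TEAE is reasonable when timing is unknown. It does not justify overriding a recorded end date.

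**Conclusion.** Wrong as written, minor in scope.

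The end-date fault holds on either reading of the trigger: an event recorded as over before Day 1 can be tabulated as a TEAE on Day 1.

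The trigger fault is conditional. Depending on the reading, 0% or 57% of enumerated year-only onsets change calendar year. The 57% assumes a full course of dosing and uniform onset. It is a share of year-only onsets, not of all adverse events, and the documents give no count of partial dates. Where a shift occurs it distorts onset timing. It distorts dose at onset mainly for former placebo and 7.5 mg BID subjects; former 25 mg BID subjects take 25 mg BID on Day 1 and in maintenance, so for them it matters only for onsets at a reduced or taper dose.

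A reader might also infer that the year shift makes treatment-emergence wrong. It does not: no enumerated on-study event changed TEAE status on either reading. Only the end-date fault does that.

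**What to change.** Amend SAP 4.1.22 before database lock:

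1. State both triggers as the month and year, or the year, of the **first** IMP dose in CVL-865-SZ-002.
2. Impute Day 1 only if the reported or latest possible end date is on or after Day 1, or the event is ongoing.
3. If the end is before Day 1, set the start to the first of the reported month, or to 1 January of the reported year. If the start is completely missing, set it to the reported end date. Classify the event as pre-treatment, and a medication as prior.
4. Never overwrite a reported date component. Confine the conflict clause to imputed end dates.
5. Say whether the algorithm applies to medications.

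The three examples in the first table then become 1 to 13 Sep 2021, 1 Jan to 20 Aug 2021, and 13 Sep 2021 for both dates, all pre-treatment. No enumerated year-only onset changes calendar year. Year-only onsets in the first-dose year still go to Day 1, up to 364 days early; that imprecision comes from year-only reporting.

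The cost is a few lines of text and a small program change, with no new data and no effect on trial conduct.

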4.1.23. Handling of Alphanumeric Data

Should there be instances where a clinical laboratory parameter is reported with imbedded non-numeric characters, as for example, “<0.1” or “>10”, the data will be imputed for quantitative summaries. The actual values as reported in the database will be presented in data listings.

For incorporation in quantitative summaries (except for concentration data), the following imputation rules will be employed:

- The lower limit of quantification will be replaced with $\frac{1}{2}$ the value of the lower limit. For example, < 0.1 will be replaced with 0.05.
- The upper limit of quantitation will be increased by one level of precision that precedes the value. For example, “>0.1” will be imputed to “0.11”, and “>10” will be imputed to “10.1”.

Additionally, the upper limit of normal (ULN)/lower limit of normal (LLN) values may be reported as alphanumeric (e.g., ‘<5’, ‘≤5’, ‘>5’, ‘≥5’). In these cases, if the ULN or LLN is necessary for determination of the laboratory severity grade, the following conventions will be employed:

If the value is in the form of ≤ 5 , the ULN will be populated with the value after removing the symbol (i.e., the ULN is set to 5). If the value is in the form of <5 , the ULN will be decreased by two levels of precision in the direction of the symbol (i.e., the ULN is set to 4.99).

If the value is in the form of ≥ 5 , the LLN will be populated with the value after removing the symbol (i.e., the LLN is set to 5). If the value is in the form of >5 , the LLN will be increased by two levels of precision in the direction of the symbol (i.e., the LLN is set to 5.01).

4.2. Analysis Periods

The start and end dates of each analysis period (following the study design) are used for the classification of efficacy data. The exact start and end of each of these periods is described for calculation purposes in [Table 3](#). Seizure frequency for each analysis period will be calculated based on [Table 3](#).

Table 3. Definition of Analysis Periods for Efficacy Data

Analysis Period	Duration	Start Date	End Date
Extension Titration Phase	~2 Weeks	Study Day, 1	The lesser of: Day 15 (Visit 2) minus 1 or **Early termination (minus 1) or End of Treatment
Extension Maintenance Phase	~52 Weeks	Day 15 (Visit 2)	The lesser of: ***Day 379 (Visit 15) minus 1 or **Early termination (minus 1) or End of Treatment
Extension Taper Phase	~3 Weeks	Day 379 (Visit 15) or **Early termination	End of Treatment

** If a subject experiences early termination from the study and continues to Taper Phase, end dates will be bound by early termination minus 1, while the start of Taper Phase will begin on the date of early termination.

*** If a subject continues to Taper Phase from Maintenance Phase

366 to 389	Day 379 (End of Maintenance Phase)	379
390 to 414	Day 400 (End of Taper Phase)	400
414 and higher	Day 428 (End of Post-treatment Follow-up)	428

Table 6. Visit Windows for Early Termination and Unscheduled Visits – mCIWA-B

Study Day of Early Termination or Unscheduled Visit	Analysis Visit	Analysis Visit Target Day
1 to 379 (on treatment, prior to Taper Phase)	Baseline	379
1 to 389 (off treatment)	Day 386 (Contact)	386
390 to 396	Day 393 (Contact)	393
397 to 403	Day 400 (End of Taper Phase)	400
403 to 417	Day 407 (Contact)	407
418 and higher	Day 428 (End of Post-treatment Follow-up)	428

Table 7. Visit Windows for Early Termination and Unscheduled Visits – PK Sampling

Study Day of Early Termination or Unscheduled Visit	Analysis Visit	Analysis Visit Target Day
1 to 141	Day 99 (Visit 5)	99
142 to 450	Day 183 (Visit 8)	183
451 and higher	Day 267 (Visit 11)	267

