#### **Number of Subjects:**

The trial population will be derived from eligible subjects from the double-blind, proof-of-concept Trial CVL-865-SZ-001. Of the approximately 150 subjects to be enrolled in Trial CVL-865-SZ-001, approximately 120 are expected to complete the trial and be eligible for enrollment in Trial CVL-865-SZ-002.

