Laboratory														
Safety laboratory blood sample	X		X		X	X	X	X	X	X	X	X	X	X
Safety laboratory urine sample	X		X		X		X			X			X	
Urine pregnancy test h	X		X		X	X	X	X	X	X	X	X	X	X

Trial Period/ Phases	Double-blind Titration Phase (2 weeks)		Maintenance Phase (52 weeks) Visits 2 through 12											
	Visit 1/BL b,c	Contact	Visit 2	Contact	Visit 3 d	Visit 4 d	Visit 5 d	Visit 6 d	Visit 7 d	Visit 8 d	Visit 9 d	Visit 10 d	Visit 11 d	Visit 12 d
Visit/Contact a	1	8	15	29	43	71	99	127	155	183	211	239	267	295
Day	0	1	2	4	6	10	14	18	22	26	30	34	38	42
Week	± 3 days													
Window														
Urine drug screening i	X													
Blood sample for PK of CVL-865 j	X						X			X			X	
Blood sample for PK of AEDs k	X						X			X			X	
Other														
IMP dispensing	X		X		X		X			X			X	
IMP compliance assessment	X	X	X	X	X	X	X	X	X	X	X	X	X	X
AED compliance assessment	X	X	X	X	X	X	X	X	X	X	X	X	X	X

Abbreviations: AED = antiepileptic drug; BL = baseline; BZD = benzodiazepine; CGI-S = Clinical Global Impression – Severity; C-SSRS = Columbia-Suicide Severity Rating Scale; ECG = electrocardiogram; ICF = informed consent form; IMP = investigational medicinal product; PGI-C = Patient Global Impression of Change; PK = pharmacokinetics.

- a. Contact with subject via phone call, internet/web, or other acceptable means of communication to check on their status.
- b. Screening/Baseline for Trial CVL-865-SZ-002 occurs at Visit 1, which is the same day as Visit 4 in Trial CVL-865-SZ-001. Any assessments conducted for Visit 4 of Trial CVL-865-SZ-001 will be considered the baseline assessments for Visit 1 of Trial CVL-865-SZ-002.
- c. Individual sites may require subjects to have COVID-19 testing done prior to enrollment. COVID-19 testing may be performed after enrollment per the investigator's discretion.
- d. In the event that a subject is unable to attend a clinic visit in person due to restrictions related to COVID-19, this visit may be completed remotely. Please refer to the Trial Operations Manual for further instructions related to remote visits.

- e. The physical examination should include weight at all time points. Physical and/or neurological examinations can be done at any time point during the trial at the investigator's discretion.

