- f. The "Since Last Visit" C-SSRS form will be completed at all visits.
- g. Adverse events (serious and non-serious) and concomitant medications should be recorded from the time of signing the ICF through the subject's last visit.
- h. For women of childbearing potential only. All positive urine pregnancy test results must be confirmed by a serum test. Pregnancy tests can be performed at any time during the trial at the discretion of the investigator if pregnancy is suspected. Monthly pregnancy tests will be required for all women of childbearing potential.
- i. The urine drug screen can be conducted at any time during the trial at the discretion of the investigator.
- j. With subjects maintaining their normal BID dosing routine, a single daytime blood sample for determination of plasma CVL-865 concentration will be collected at Visits 5, 8, and 11. The date and time of the PK sample, as well as the time of ingestion of the morning dose of IMP (on the same day), will be recorded in the source documentation.
- k. One 5-mL sample for each adjunctive AED collected at Visits 5, 8, and 11.

**Table 3 Schedule of Assessments - Maintenance Phase (Visits 13 Through 15/ET Only), Taper Phase, and Post-treatment Follow-up Phase**

Trial Period/ Phases	Maintenance Phase (52 weeks) Visits 13 through 15/ET			Taper Phase (3 weeks)			Post-treatment Follow-up	
	Visit 13 b	Visit 14 b	Visit 15/ET c	Contact	Contact	Visit 16 b	Contact	Visit 17
Visit/Contact a	Visit 13 b	Visit 14 b	Visit 15/ET c	Contact	Contact	Visit 16 b	Contact	Visit 17
Day	323	351	379	386	393	400	407	428
Week	46	50	54	55	56	57	58	~61
Window	± 3 days							
Entrance and History								
Review of birth control methods	X	X	X	X	X	X	X	X
Efficacy Assessments								
Review eDiary including compliance with use of eDiary	X	X	X	X	X	X	X	X
PGI-C			X					
CGI-S			X					
Safety Assessments								
Physical/neurological examination d			X			X		
ECG			X			X		
Vital sign measurements			X			X		
C-SSRS e			X			X		X
mCIWA-B			X	X	X	X	X	X
Prior/concomitant treatments including BZD use f	←-----→							
Adverse event monitoring f	←-----→							
Laboratory								
Safety laboratory blood sample	X	X	X			X		X
Safety laboratory urine sample			X			X		
Urine pregnancy test g	X	X	X			X		

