#### **9.4.3     *Other Analyses***

The CVL-865 concentration data will be used to determine the extent to which subjects attain exposure levels within the range predicted at each dosing regimen. Likewise, the AED concentration data will be used to review the exposure levels of AED taken with or without CVL-865. Appropriate tabular and/or graphical summaries of all PK concentration data will be generated as detailed in the SAP.

Concentration data from this trial may be used to update the previously established population PK model for CVL-865. Any population PK analysis (if completed) will be presented separately from the main CSR.

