3.3. Pharmacokinetics

To evaluate the plasma exposure of CVL-865 (and anti-epileptic drug, if appropriate), a single daytime blood sample will be collected at Visits 1, 5, 8, and 11. The date and time of the pharmacokinetic (PK) sample, as well as the time of ingestion of the morning dose of IMP (on the same day), will be recorded in the source documentation.

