5.13. Pharmacokinetics

5.13.1. Pharmacokinetic Sampling

With subjects maintaining their normal BID dosing routine, a single daytime blood sample for determination of plasma CVL-865 concentration will be collected at Visits 5, 8, and 11. The date and time of the PK sample, as well as the time of ingestion of the morning dose of IMP (on the same day), will be recorded in the source documentation.

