5.13.2. Pharmacokinetic Analysis

Plasma concentrations of CVL-865 in unit as reported by the analytical laboratory will be summarized by nominal time point using descriptive statistics. Summaries will include mean, standard deviation and coefficient of variation, median, minimum, maximum, and geometric mean.

Concentration values that are below the level of quantification (BLQ) will be set to zero for summary tables. The geometric mean, however, will be calculated by imputing BLQ values as $\frac{1}{2}$ BLQ. Individual values that are BLQ will be presented as “BLQ” in the concentration data listing.

Concentration data from this trial may be used to update the previously established population PK model for CVL-865. In addition, the relationship between the exposure levels (or dose) of CVL-865 and one or more efficacy/safety endpoints may be evaluated for the purpose of exploratory PK/pharmacodynamic analyses. Any population PK analysis and exploratory biomarker analyses (if completed) will be presented separately from the main clinical study report.

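### SAP Table 7 assigns early-termination and unscheduled CVL-865 samples to Visits 5, 8 or 11 by a faulty rule, while neither schedule plans a sample at Visit 15/ET and the documents disagree on Visit 1

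*SAP*

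**What the plan says.** **Sampling times.** Footnote j to protocol Table 2 says that "a single daytime blood sample for determination of plasma CVL-865 concentration will be collected at Visits 5, 8, and 11", which are Days 99, 183 and 267. SAP 5.13.1 agrees: "plasma CVL-865 concentration will be collected at Visits 5, 8, and 11". However, the grid row "Blood sample for PK of CVL-865" in protocol Table 2 also has a mark at Visit 1, as does SAP Table 9, and SAP 3.3 says "a single daytime blood sample will be collected at Visits 1, 5, 8, and 11".

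**Early termination.** Protocol Table 3 and SAP Table 10 contain Visit 15/ET. Both mark a safety blood sample there and neither has a pharmacokinetic row.

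**Windows.** SAP Table 7, "Visit Windows for Early Termination and Unscheduled Visits – PK Sampling", sends Days 1 to 141 to Visit 5, Days 142 to 450 to Visit 8, and Day 451 onward to Visit 11. The text of SAP 4.3 cites Tables 4, 5 and 6 but not Table 7.

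**Use of the data.** Protocol 9.4.3 would use the concentrations to "determine the extent to which subjects attain exposure levels within the range predicted at each dosing regimen". SAP 5.13.2 summarises them by nominal time point and adds that "the relationship between the exposure levels (or dose) of CVL-865 and one or more efficacy/safety endpoints may be evaluated". The endpoint in protocol Section 3 is an exploratory listing by dose and visit.

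**The concern.** Table 7 decides where an early-termination sample is counted, yet no schedule asks for one. The first planned concentration on the extension regimen is at Day 99, so subjects who stop in the first 14 weeks have none. In a trial whose primary objective is safety and tolerability, these are subjects whose exposure one would want to know.

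If such a sample does exist, Table 7 labels it misleadingly. A titration-phase value would be reported as a Visit 5 value, and a sample taken around Day 267 as a Visit 8 value. At stake are the meaning of the by-visit concentration summary, the statement on attained exposure, and any later exposure-response work that uses the same visit labels.

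**Working it through.** **1. What a subject who stops before Visit 5 contributes.** The scheduled on-extension days are 99, 183 and 267, with a ±3-day window, so the earliest planned sample is at Day 96. None is scheduled at Visit 15/ET. Scheduled on-extension concentrations for such a subject: 0. Visit 1 falls on the same day as Visit 4 of SZ-001 (protocol Table 2, footnote b), so a sample there describes the SZ-001 regimen.

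**2. Table 7 boundaries, checked as midpoints of the target days.**

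| Boundary | Midpoint | Table 7 |
|---|---|---|
| Visit 5 / Visit 8 | (99 + 183) / 2 = 141 | 141 |
| Visit 8 / Visit 11 | (183 + 267) / 2 = 225 | 450 |

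The printed 450 equals 183 + 267, the sum without the halving. The last planned day is 428, or 431 with the window, and 431 < 451. No off-schedule sample within the planned duration can reach Visit 11, and every one from Day 142 onward goes to Visit 8, including taper and follow-up samples. SAP 4.3 prefers a scheduled value within a visit. A replacement draw at Day 270 for a missed Visit 11 would therefore go to Visit 8, lose to the scheduled Visit 8 value, and appear in no visit summary.

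**3. Doses mixed in the first window.** Protocol Table 4 gives titration doses of 5 and 12.5 mg BID (former placebo), 12.5 and 17.5 mg BID (former 7.5 mg BID) and 25 mg BID (former 25 mg BID). Maintenance is at 25 mg BID, reducible to 17.5 mg BID. A sample from the first titration week could thus be filed under Visit 5 at a dose up to 25 / 5 = 5 times lower than the Maintenance dose. An early stopper has no scheduled Visit 5 value to override it.

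**4. How many subjects.** The documents give no dropout rate for the extension, so both ranges are assumptions.

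- *Rate borrowed from SZ-001.* Of about 150 subjects, "approximately 120 are expected to complete the trial and be eligible for enrollment in Trial CVL-865-SZ-002", a loss of 20% over 13 weeks. With a constant hazard, ln(150/120) = 0.2231 and 1 − exp(−0.2231 × 14/13) = 21.4%, or 25.6 of 120 before Day 99. Half the hazard gives 11.3%, or 13.6 of 120.
- *Total discontinuation of 10% to 50% over the 378 days before taper.* 1 − (1 − total)^(98/378) gives 2.7% to 16.4%, or about 3 to 20 of 120.

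**5. Size of a possible bias.** Assume log-normal exposure with CV 40%, so SD(log) = √ln(1 + 0.4²) = 0.385. Let z be standardised log exposure and P(stop) = logit⁻¹(a + ln(OR) · z), with a chosen to give the overall loss. The bias in the geometric mean of those sampled is exp(0.385 × E[z | stayed]) − 1.

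| OR of stopping per SD | 11.3% lost | 21.4% lost |
|---|---|---|
| 3 | −4.1% | −7.3% |
| 2 | −2.8% | −5.1% |
| 1.5 | −1.7% | −3.2% |
| 1 | 0 | 0 |
| 0.5 | +2.9% | +5.4% |

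The standard error of the log mean is 0.385/√106.4 = 0.037 and 0.385/√94.4 = 0.040, so at OR 2 the bias is 0.77 to 1.33 standard errors. Neither the CV nor any odds ratio comes from the documents. Single daytime draws at an unfixed time after dose would vary more. If the concentration CV were 60% to 80%, the extra variation being unrelated to stopping, the same bias would be about 0.4 to 0.9 standard errors.

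**The case against.** **Table 7 need not contradict the schedule.** Its title has the same form as those of Tables 4 to 6, and providing a window for a sample that might arise does not mean that one is planned. This stands. The absence of an ET sample is a gap in the design, and the faults in Table 7 are its dose pooling and its second boundary.

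**Early stoppers are not wholly without data.** If Visit 1 is sampled, a former 25 mg BID subject has a value on the regimen used in the extension. The PK analysis set in SAP Table 8 needs one measurable concentration and does not require it to be post-baseline. Days on IMP and cumulative dose are recorded for all, and adverse events are presented by dose at onset. This also stands. It does not help former placebo or 7.5 mg BID subjects, and it depends on the Visit 1 question that the documents leave open.

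**Missing subjects are already handled.** SAP Table 8 leaves out subjects with no measurable concentration, and SAP 9.3 requires the contributing count in each summary. Much of any added reporting can therefore be derived from planned outputs.

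**A stronger reading is tempting:** that attained exposure is understated and any exposure-adverse-event relation weakened, because subjects with high exposure leave first. The documents do not support a direction. Protocol 7.3 also names dissatisfaction with treatment as a reason to stop, which could go with low exposure. Exclusion criterion 2 removes subjects who tolerated SZ-001 poorly, and the 20% figure mixes non-completion with ineligibility. The exposure-response analysis is optional.

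**Conclusion.** The point holds as a low-priority correction. Three things follow from the documents without assumption:

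- No CVL-865 sample is scheduled at Visit 15/ET, and the first scheduled on-extension sample is at Day 99.
- The documents disagree on Visit 1.
- Table 7 pools doses in its first window, and its Visit 11 window cannot be reached within the planned 428 days.

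The effect on estimated exposure is unknown in size and sign. It is about 1.7% to 7% low in the geometric mean if higher exposure raises stopping (CV 40%, odds ratio 1.5 to 3 per SD, 11% to 21% lost), similar in the other direction if lower exposure does, and zero with no link. These figures are illustrations of scale. A claim that exposure is understated, or that early stoppers contribute nothing, goes beyond the documents. With no hypothesis and an exploratory endpoint, no formal conclusion of the trial depends on this.

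**What to change.** 1. **SAP Table 7 and 5.13.2.** Summarise early-termination and other off-schedule samples as a separate time point, by actual dose at sampling, and not under Visits 5, 8 or 11. If windows are kept, change the second boundary to 225/226 and cite Table 7 in SAP 4.3. Cost: SAP text and one table row. The daily dose is already on the exposure CRF.
2. **Visit 1.** Reconcile protocol Table 2 and its footnote j with SAP Table 9 and its footnote j, SAP 3.3 and SAP 5.13.1. Cost: text only.
3. **Visit 15/ET, if early-termination visits are still to come.** Assign a concentration tube to the blood already drawn there for early terminators, and record the time and dose of the last IMP. Cost: a schedule and laboratory-manual line in an amendment and a small assay cost. Subjects who have interrupted IMP or do not attend will still be missed, and a titration-phase sample says little about 25 mg BID.
4. **Interpretation.** State in SAP 5.13.2 that exposure at each visit describes subjects who reached that visit. Cost: one sentence.

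Items 1, 2 and 4 need no new sample and can be made at any time before database lock.
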